	 Change from baseline in the number of monthly days with use of acute migraine medication Change from baseline in the number of monthly migraine days with use of acute migraine medication PGIC score Change from baseline in the number of monthly migraine days in patients with MOH MBS score Change from baseline in monthly number of Migraine attacks for each 12-week period Change from baseline in monthly number of Headache episodes for each 12-week period Change from baseline in the MSQ v2.1 sub-scores Change from baseline in the EQ-5D-5L VAS score HCRU Change from baseline in the WPAI sub-scores
 Safety Objective To evaluate the safety and tolerability of eptinezumab To evaluate the long-term safety and tolerability of eptinezumab 	 Safety Endpoints Adverse events Absolute values and changes from baseline in clinical safety laboratory test values, vital signs, weight, and ECG parameter values Potentially clinically significant clinical safety laboratory test values, vital signs, weight changes, and ECG parameter values Development of specific anti-eptinezumab antibodies (ADA) including neutralizing antibodies (NAbs) Columbia-Suicide Severity Rating Scale (C-SSRS) score

2 Study Design

This is an interventional, multi-national, multi-site, randomized, double-blind, placebocontrolled Phase IIIb study designed to demonstrate efficacy and safety of eptinezumab for migraine prevention in patients with unsuccessful prior preventive treatments. The placebocontrolled period will be followed by an extension period where all patients will receive active treatment to assess the long-term safety, tolerability and effect of eptinezumab.

The target population for this study is defined as patients with chronic migraine (CM) or episodic migraine (EM), as outlined in the IHS ICHD-3 guidelines¹ with documented evidence of migraine occurring on \geq 4 days per month prior to screening as confirmed via prospectively collected information in the eDiary during the Screening Period, and with documented evidence of failure to 2-4 different preventive migraine medications in the past 10 years. The aim is that approximately 40% of the randomized patients are patients with EM.

It is planned that 840 patients will be randomly allocated to one of three treatment groups: eptinezumab 300 mg, eptinezumab 100 mg, or placebo, in a ratio of 1:1:1.

Randomization will be stratified by country and monthly headache days (MHDs) at baseline (\leq 14 MHDs/>14 MHDs).

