12.1 General Efficacy Analysis Methodology

Unless otherwise specified, all the efficacy analyses for the Placebo-controlled Period will be based on the FAS and all the efficacy analyses for the Extension Period will be based on the FAS_LT.

All the tables and graphs will be presented by treatment group for the Placebo-controlled Period and both by treatment group and treatment sequence group for the Extension Period.

All the p-values will be based on two-sided tests; the confidence intervals (CIs) will be twosided; and the endpoints not included in the testing strategy will be presented with nominal pvalues and 95% CIs.

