12.2 Testing Strategy

The testing strategy will be a sequence of tests, either testing one endpoint at a time or using Bonferroni-Holm to test a group of endpoints. Only if one step has shown a statistically significant effect will the formal testing continue with the next step, thus ensuring protection of the type 1 error. The steps are described below. A graphical representation of the testing strategy can be found in Panel 3.

A significance level of 0.05 will be used. The significance level is denoted by α below.

Step 1

Test the primary endpoint change from baseline in MMDs (Weeks 1-12) for the 300 mg dose compared to placebo on a significance level of α . Only if the p-value $<\alpha$ in favour of the 300 mg dose is the effect considered statistically significant and the testing continues with the next step.

Step 2

Test the key secondary endpoint 50% responders for MMD (Weeks 1-12) for the 300 mg dose compared to placebo, using a significance level of α . Only if the p-value $<\alpha$ in favour of the 300 mg dose is the effect considered statistically significant and the testing continues with the next step.

Step 3

Test the primary endpoint change from baseline in MMDs (Weeks 1-12) for the 100 mg dose compared to placebo on a significance level of α . Only if the p-value $<\alpha$ in favour of the 100 mg dose is the effect considered statistically significant and the testing continues with the next step.

Step 4

Test the key secondary endpoint 50% responders for MMD (Weeks 1-12) for the 100 mg dose compared to placebo, using a significance level of α . Only if the p-value $<\alpha$ in favour of the 100 mg dose is the effect considered statistically significant and the testing continues with the next step.

Step 5

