12.3 Analysis Methodology for the Primary Endpoint

12.3.1 Primary Estimand

A summary of the intercurrent events that will be addressed and the estimand attributes can be found below. Further details on the intercurrent events and the strategies used to address them are given in Section 12.3.3.

The primary estimand will be the effect of eptinezumab on number of monthly migraine days that would be seen in the hypothetical case where no acute medication was available, if patients withdrawing due to lack of efficacy remained on their current trajectory, if patients withdrawing due to adverse events at an early stage were considered as obtaining only limited improvement to their baseline disease level, and if the effect was considered regardless of use of preventive medication and infusion interruptions or terminations.

Intercurrent events that will be addressed:

- Use of acute medication to treat a headache
- Use of preventive migraine medication
- Withdrawal due to lack of efficacy
- Withdrawal due to adverse event
- Withdrawal due to other reasons
- Interruption/termination of infusions

Attributes of the primary estimand:

• The **treatment** condition of interest is eptinezumab (both 300 mg and 100 mg) compared to placebo

- The **population** is all patients that fulfil the inclusion and none of the exclusion criteria for the study
- The **endpoint** to be considered is the change from baseline in MMDs across weeks 1-12
- The **population-level summary** is the least squares mean difference between eptinezumab and placebo for the endpoint

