12.3.3 Strategies for Addressing Intercurrent Events in Primary Estimand

Use of acute medication to treat a headache

When patients complete a headache in the headache eDiary they are asked whether they took any medications to treat the headache. In case of an affirmative answer, they are asked the question "*Did you take this medication because you believed that you were having a migraine*?". In a hypothetical scenario where medication is not available, it is hypothesised that patients that answer this question with a "*Yes*" would have experienced a migraine.

Thereby, a hypothetical strategy is used to address the intercurrent event of use of acute medication by counting a day where patients took medication because they believed they were experiencing a migraine as a migraine day, using the definition given in Section 4.5.1.

Use of preventive migraine medication

Initiating a new preventive migraine treatment and concomitant use of preventive migraine treatment at study entry is generally disallowed in the study, see the *Clinical Study Protocol*, Appendix II.

A treatment policy strategy is used to address the intercurrent event of use of preventive migraine medication by using the data collected regardless of whether or not the patient uses preventive migraine treatment.

Withdrawal due to lack of efficacy

It is hypothesised that patients withdrawing due to lack of efficacy will remain on their current level of MMDs after withdrawing at least until 12 weeks after their first dose.

Therefore, the intercurrent event of experiencing lack of efficacy resulting in a patient withdrawing, will be addressed using a hypothetical strategy. In the hypothetical world where patients would not drop out due to lack of efficacy, it is hypothesised that the patients would continue on their current unsatisfactory symptom level, so imputation of missing data in this situation aim to ensure that the current symptom level is used for the analysis even if very little data is available. See details of the implementation in the rules for handling missing data described in Section 19.1.1.

Withdrawal due to adverse event

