It is hypothesised that patients withdrawing very early in the study (during the first 4 weeks after first IMP infusion) due to adverse events have not been successfully treated. Therefore, in a situation where a patient withdraws during the first 4 weeks after first IMP infusion and the amount of data collected through the eDiary is not sufficient to derive a monthly score using the general derivation rules, the missing data is penalized to reflect that the symptom level will be close to the expected higher level of MMDs that was experienced at Baseline.

Patients withdrawing due to adverse events later in the study are hypothesised to behave similarly to the study population as a whole.

Details of the imputations used can be seen in the rules for handling missing data described in Section 19.1.1.

Withdrawal due to other reasons

Withdrawals due to other reasons than lack of efficacy or adverse events will be handled with a treatment policy strategy using the data collected regardless of the intercurrent event and using the imputation rules specified in Section 19.1.1.

Interruption/termination of infusions

If interruption or termination of infusion leads to withdrawal, it is handled according to the rules above.

Temporary interruption of infusion is not expected to impact the efficacy data. Premature termination of infusion (that is, only receiving a partial infusion) could impact the efficacy. However, it is expected that the implications of a partial infusion will be reflected in the collected eDiary data.

Hence, the intercurrent events of temporary infusion interruptions, premature terminations of infusions, and complete termination of infusions not leading to withdrawal will be addressed using a treatment policy strategy by using the data collected regardless of these intercurrent events.

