19.1.1.1 Monthly Migraine Days (MMDs)/Monthly Headache Days (MHDs)

The following describes the derivation of MMDs. The derivation of MHDs follows the same principles.

4-Week Intervals

For Baseline and each 4-week period post-baseline in the study, the number of MMDs will be derived as the number of migraine days within each 28-day interval using the imputation rules described below. The 4-week periods post-baseline that are considered are the following: Weeks 1-4, Weeks 5-8, Weeks 9-12, Weeks 13-16, Weeks 17-20, Weeks 21-24, Weeks 25-28, Weeks 29-32, Weeks 33-36, Weeks 37-40, Weeks 41-44, Weeks 45-48, Weeks 49-52, Weeks 53-56, Weeks 57-60, Weeks 61-64, Weeks 65-68, Weeks 69-72.

In general, for 4-week periods where the eDiary is completed on at least 14 days out of the 28 days, prorating will be used to calculate the MMDs, and for 4-week periods where the eDiary is completed on less than 14 days out of the 28 days, the MMDs will be set to missing. However, there are cases where weighting will be used when less than 14 days have been completed, and an overview is given in Panel 5.

Prorating

Intended to be used for 4-week periods where the eDiary is completed on at least 14 out of the 28 days, the prorating procedure consists of imputing days with missing information with the observed mean number of migraine days in the period as follows:

28*(Reported Migraine Days/Reported eDiary Days)

This imputation rule will also be used for the Baseline value regardless of the number of reported eDiary days in the screening period. Patients are, however, required to demonstrate compliance with the eDiary and fill it out for at least 24 out of the 28 days in the screening period in order to be eligible for randomization.

Weighting

Intended to be used in special cases for the first 4-week period post-baseline, where the eDiary is completed on less than 14 days out of the 28 days due to withdrawal. When weighting is used, the number of MMDs is derived as a weighted sum of the observed mean number of migraine days in the period and the mean MMDs for the preceding period as follows:

$$28*(W*X + (1 - W)*X_p),$$

where $W = Reported \ eDiary \ Days/13$, $X = Reported \ Migraine \ Days/Reported \ eDiary \ Days$, and $X_p = preceding \ MMDs/28$.

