Patients who withdraw due to lack of efficacy so early that they only have post-baseline data from Weeks 1-4 will have their MMDs calculated using weighting for Weeks 1-4 if they have less than 14 days of eDiary reporting during the first 4 weeks of the study. If they have 14 days or more in this period, their MMDs for Weeks 1-4 will be calculated using prorating.

Patients who withdraw due to adverse events so early that they only have post-baseline data from Weeks 1-4 will have their MMDs calculated using weighting for Weeks 1-4 if they have less than 14 days of eDiary reporting during the first 4 weeks of the study. If they have 14 days or more in this period, their MMDs for Weeks 1-4 will be calculated using prorating.

	Number of Reported eDiary Days		ed eDiary Days in Period
Description	4-Week Period	0-13	14-28
All patients randomized	Baseline	Prorating*	Prorating
Patients not withdrawing due to lack of efficacy/adverse event	Weeks 1-4	None (missing)	Prorating
Patients not withdrawing due to lack of efficacy/adverse event	4-week periods after week 4	None (missing)	Prorating
Patients withdrawing due to lack of efficacy	Weeks 1-4	Weighting	Prorating
Patients withdrawing due to lack of efficacy	4-week periods after week 4	None (missing)	Prorating
Patients withdrawing due to adverse event	Weeks 1-4	Weighting	Prorating
Patients withdrawing due to adverse event	4-week periods after week 4	None (missing)	Prorating

Panel 5 Overview of Imputation Rules for 4-Week Periods for eDiary Data

*Patients are required to complete the eDiary for at least 24 days during the first 28 days of screening to be eligible

In case of a reporting day where a patient answers in the evening diary that they experienced a headache on that day but then never fills out an actual headache in the headache diary, the day will be assigned as a no headache and no migraine day.

When the number of MMDs have been calculated for a given 4-week period, the result will be rounded to two decimals.

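### No rule holds lack-of-efficacy withdrawals at their current level after Week 4, and the Weeks 1-4 weighting rule has inconsistent triggers and no value at zero diary days

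*SAP*

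**What the plan says.** **Estimand.** SAP 12.3.1 defines the effect partly by what would be seen "if patients withdrawing due to lack of efficacy remained on their current trajectory". SAP 12.3.3 calls this a hypothetical strategy and assumes that these patients "will remain on their current level of MMDs after withdrawing at least until 12 weeks after their first dose". It says the imputation is meant to bring the current symptom level into the analysis even when data are sparse, and points to 19.1.1. Adverse-event withdrawals are handled differently. Their missing data are penalised toward baseline "in a situation where a patient withdraws during the first 4 weeks after first IMP infusion" with too little diary data for the general rule. Later adverse-event withdrawals are assumed to resemble the whole study population.

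**Derivation.** SAP 19.1.1.1 prorates months with at least 14 diary days. Otherwise, "for 4-week periods where the eDiary is completed on less than 14 days out of the 28 days, the MMDs will be set to missing". The exception is a weighted Weeks 1-4 value. The text gives it to "Patients who withdraw due to adverse events so early that they only have post-baseline data from Weeks 1-4" and to lack-of-efficacy withdrawals described in the same way. After Week 4, the Panel 5 rows for lack of efficacy, adverse events and everyone else are identical: missing at 0-13 days, prorated at 14-28.

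**Analysis.** The primary MMRM (SAP 12.3.2) uses the monthly scores that are available. SAP 2 expects withdrawn patients to keep the diary until a visit 12 weeks after the last dose, unless they withdraw consent. Protocol 8.9 limits new information after withdrawal to that visit and adverse-event follow-up.

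**The concern.** The SAP makes two different assumptions about late withdrawals (no further improvement after lack of efficacy; typical behaviour after an adverse event) and gives both the same derivation. That derivation matches the second assumption. For lack of efficacy, the primary analysis then estimates something other than the stated estimand wherever diary data stop. The responder endpoints in 19.1.1.2 average the available months, so they do in effect keep such a patient at the last observed level. The same patient is therefore treated differently in two tested endpoints.

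The weighting rule is meant to stop very early failures from being lost. If its trigger depends on which section is read, two programmers can build different primary datasets. If it returns nothing at zero diary days, the patients it was written for may be the ones dropped.

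**Working it through.** **1. The plan's own figure.** Inputs from SAP 16: 280 per arm, 2% without a post-baseline value (274 left), 40% EM and 60% CM, with the stated effects and SDs; alpha 0.05 two-sided (SAP 12.1, 12.2).
- SD = √(0.4×3.1² + 0.6×5.8²) = 4.902
- 100 mg: 0.4×0.69 + 0.6×2.03 = 1.494, power 94.6% (stated about 94%)
- 300 mg: 0.4×1.11 + 0.6×2.60 = 2.004, power 99.8% (stated 99%)

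The stated power is reproduced and does not depend on the disputed rule.

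**2. One patient.** Withdrawal for lack of efficacy after month 1; months 2 and 3 missing. The MMRM's implied value is the arm mean plus ρ × (own month 1 − arm month 1 mean), so the shortfall against a held level is (1−ρ) of the patient's residual. The correlation ρ is an assumption, and 4.902 stands in for the monthly SD. For a patient one SD worse than the arm mean (4.9 days):

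| ρ | Held residual | MMRM-implied residual | Gap in Weeks 1-12 average, ⅔(1−ρ)×4.902 |
|---|---|---|---|
| 0.5 | 4.9 | 2.45 | 1.63 |
| 0.7 | 4.9 | 3.43 | 0.98 |
| 0.85 | 4.9 | 4.17 | 0.49 |

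**3. Treatment difference, by hand.** Assume a patient at −0.5 in month 1, with arm means of −4.5 then −5.0. The implied later value is −5 + ρ×4: −2.6, −2.0 or −1.6 at ρ = 0.6, 0.75 or 0.85, a gap of 2.1 to 1.1 days. With rates one percentage point apart, 0.01 × ⅔ × (1.1 to 2.1) = 0.007 to 0.014, or about 0.01 day.

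**4. Treatment difference, by simulation.** 400,000 patients per arm, true difference 1.494, withdrawals taken from the worst month 1 values. Change in the estimated difference when the level is held instead of left to the MMRM:

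| Lack-of-efficacy rate, placebo v active (assumed) | ρ=0.5 | ρ=0.7 | ρ=0.85 |
|---|---|---|---|
| 2% v 1% | 0.04 | 0.02 | 0.01 |
| 5% v 1% | 0.13 | 0.08 | 0.04 |
| 10% v 3% | 0.18 | 0.11 | 0.05 |
| 5% v 5% | 0.00 | 0.00 | 0.00 |

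Holding widens the difference when placebo has more such withdrawals and narrows it when active has more. In these runs power for 100 mg is 94-95% under the MMRM and 94-98% when held.

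**5. Triggers.** Test case: withdrawal on Day 20, 10 diary days in Weeks 1-4, diary then resumed to Week 12.

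| Place | Trigger | Weeks 1-4 value |
|---|---|---|
| 12.3.3 (adverse events only) | withdrawal in the first 4 weeks, too little data | penalised |
| 19.1.1.4 (both reasons) | withdrawal within 28 days, under 14 days | weighted |
| 19.1.1.1 text | only Weeks 1-4 data exist | missing |
| Panel 5 | withdrawal for that reason, 0-13 days, no time limit | weighted |

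**6. Zero diary days.** With D reported days and M migraine days, the value is 28×(W×X + (1−W)×Xp), where W = D/13 and X = M/D. At D = 0, X is 0/0. Since W×X = M/13, the simplified form gives 28×Xp, the baseline MMDs. For a baseline of 14 this is 14 at D = 0, and 12.92 or 15.08 at D = 1 (no migraine or migraine that day). Baseline is thus the natural limit, but the SAP does not say so.

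**7. Sensitivity analyses (12.3.5).** One removes the Weeks 1-4 weighting; the other extends it to everyone with under 14 days. Neither changes a month after Week 4.

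**The case against.** Several stronger readings are tempting, and the documents do not support them.

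- A reader might infer that every lack-of-efficacy month after Week 4 is missing. Panel 5 prorates any month with 14 or more diary days, and SAP 2 expects the diary to run to Week 12 for a patient dosed once. The gap concerns patients who also stop the diary. Post-withdrawal months that are observed enter as collected, which is not a held level either.
- A reader might infer that the MMRM discards the patient's own level. With unstructured covariance it keeps a share ρ of the residual.
- A reader might extend the fault to the Weeks 13-24 endpoint. The horizon 12.3.3 commits to is Week 12; going further rests only on 12.4.1 framing the key secondary estimands similarly.
- Panel 5 alone suggests that a Week 20 withdrawal with a sparse first diary month gets a weighted value. The 19.1.1.1 text, which ties the sparse diary to withdrawal, and the 28-day wording in 19.1.1.4 exclude this.
- A reader might infer that zero-day patients are always lost. That needs literal coding and no valid month in Weeks 5-12, because the FAS requires only one valid month in Weeks 1-12.

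It is also fair that 12.3.3 speaks of an aim, and that the size is slight against planned effects of 0.69 to 2.60 days. What stands is that no rule holds the level after Week 4, the triggers are not equivalent, the zero-day value is undefined, and no planned analysis tests the held level.

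**Conclusion.** The point holds as a mismatch between estimand and derivation, and as an ambiguity in how the primary endpoint is derived. It is not a threat to the primary result. For lack-of-efficacy withdrawals, months after Week 4 with fewer than 14 diary days are handled under missing at random, contrary to 12.3.1 and 12.3.3. The likely effect on the treatment difference is about 0.01 day, or 0.01 to 0.04 at 2% v 1% if withdrawals come from the worst tail. It reaches 0.04 to 0.18 day only under the assumed rates of 5% v 1% or 10% v 3%, and is about zero with equal rates. Power is not affected. All of these sizes rest on assumed withdrawal rates and correlations, which the documents do not give. The trigger conflict and the zero-day gap concern few patients, but both should be settled because they decide who has a Weeks 1-4 value and, in some cases, who is in the FAS.

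**What to change.** 1. **Make estimand and rule agree.** Either restate 12.3.1 and 12.3.3 so that lack-of-efficacy months missing after Week 4 are handled under missing at random by the MMRM, and add a sensitivity analysis that holds the last derived month through Week 12; or put that hold rule, through Week 12 only, into Panel 5.
2. **Use one trigger** in 12.3.3, 19.1.1.1, 19.1.1.4 and Panel 5: withdrawal for lack of efficacy or adverse event within 28 days of first infusion, with fewer than 14 reported days in Weeks 1-4. Say what applies when the withdrawal date is missing, since 19.3.2 does not impute it.
3. **Define zero days.** Write the weighted value as 28×(Reported Migraine Days/13 + (1−W)×Xp), so that no reported days gives baseline MMDs, and state that this counts as a valid Weeks 1-4 value for the FAS.
4. **Reconcile** SAP 2 with Protocol 8.9 on diary data after withdrawal.

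The change summary in protocol edition 3.0 suggests the Placebo-controlled Period may already be unblinded. If so, document the rule as programmed and add the held-level analysis as a sensitivity analysis only. The cost is SAP wording, a few lines of derivation code and one extra model run.
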